### **8.4 SUBJECT RECRUITMENT**

Subjects will be recruited in the United State by a clinical research recruiter and/or through advertisement at outdoor locations (i.e. flea markets, outside of movie theaters, shopping malls, train stations, stores that sell cigarettes), print media (i.e., local newspapers, billboards), and web media (e.g. Craigslist, Facebook, Task Rabbit, Google Ads) [REDACTED]. Potential subjects will convey their interest in participating in the study by calling or emailing study personnel using the contact information provided in the recruitment materials, or responding to outreach from the clinical recruiter.

All study participants will undergo a screening call where they will be asked questions to confirm study eligibility. During this call, study personnel will inform the potential subject of the study details and will answer any questions. Eligible participants who meet the inclusion/exclusion criteria will be offered the opportunity to participate in the study. Potential subjects will then determine if they would like to proceed with scheduling, and if so, study personnel will schedule the subject for a test session. At the test session, an Informed Consent Form [REDACTED] will be signed prior to participation.

### **8.5 SUBJECT STIPEND**

Participants will be compensated \$100 in the form of a Visa Gift card for the test session lasting approximately 60 minutes. Participants will be compensated at the end of their study session.

### **8.6 SAMPLE SIZE AND JUSTIFICATION**

Per FDA Guidance (US Food and Drug Administration (FDA), 2016) and HE75 – Human factors engineering – Design of medical devices (ANSI/AAMI, 2013), a Usability Validation Study should include at least fifteen (15) participants of each user group. Since

the Pivot Breath Sensor has one (1) user group and no critical tasks were identified, this study will include up to 15 subjects. This sample size is expected to provide adequate data to assess the human factors and usability of the Pivot Breath Sensor.

### **8.7 STUDY ARTICLES**

Pivot Breath Sensor in representative packaging [REDACTED] that includes:

- Pivot Breath Sensor
- USB charging Cable
- Replaceable Mouthpiece
- Quick Start Guide [REDACTED]
- User Manual (available on an iPad)

In addition, the testing room will be equipped with electrical outlets and a charging cube.

### **8.8 EQUIPMENT AND MATERIALS**

- A pre-set Pivot Breath Sensor with example CO breath samples, or a CO Log Print Out
- Printed prompt cards for the participant to reference during each task
- Timer or clock
- Video recording equipment
- Camera
- Post-it notes
- Quick Start Guide for Observer/ Moderator
- User Manual (printed) for Observer/ Moderator
- Electronic Surveys
- Case Report Forms

A full list of equipment and materials used during the study will be recorded in the report.

### **8.9 USER MANUAL AND TRAINING**

The Pivot Breath Sensor was designed to be as intuitive as possible, such that users are able to understand how to use the product on their own. No in-person training is formally offered to Pivot Breath Sensor users. A Quick Start Guide and package labeling is included with the device and an online User Manual is also available to aid the user. All of these items will be accessible to the study participant plus a phone and a phone number within the labeling material to contact technical support. Since in-person training will not be formally offered to all users who purchase the Pivot Breath Sensor, in-person training will not be included in this study. Study participants will have access to the aforementioned materials. Any instance of participants referring to the User Manual,

---

 In previous usability testing, two subgroups of users used a similar, predecessor breath sensor, with one subgroup including 18 to 49-year-olds, and with the other subgroup including 50 to 80-year-olds. User performance was compared between the two subgroups, and no statistical difference was identified between the two cohorts for any of the tasks, except for accessing the CO Breath Sensor Frequently Asked Questions (FAQs). Based on previous testing, it was concluded that age is not significant enough of a contributing factor to require two separate user profiles in usability validation testing for this product. As such, a single user group consisting of participants with a range of ages will be tested as part of this study.

Quick Start Guide or packaging during the study will be recorded.

While participants will have the User Manual, Quick Start Guide and packaging available to them at any point during the study, they will not be asked to read instructions (except during the knowledge questions covered in the User Documentation Assessment – see Section 11.2) or use any of the forms of training available.

## **8.10 TEST ENVIRONMENT**

The study will be performed in an office building conference room or office.

### **8.10.1 Location testing will be performed:**

The location of testing will either be at the Carrot Inc. office [REDACTED] or equivalent. For example, office space may be rented to be nearer to test subjects.

## **8.11 STUDY PERSONNEL**

The study team members will be trained by reading the study protocol and reviewing the case report forms. The study team members will have full training on the operation of the study devices.

The following roles will be fulfilled by Carrot Inc. employees and consultants during the study:

- Study Moderator – Responsible for moderating the study, delivering instructions (as needed) and ensuring that participants progress from one use scenario to the next, and asking questions to probe about observed use errors and close calls.
- Study Facilitator – Responsible for organizing the simulated environment, study articles, equipment, and required documentation (e.g. informed consent form, non-disclosure agreements).
- Study Observer(s) – Responsible for taking notes during the study sessions and documenting key events of the study as they occur.
- Technical Support – Responsible for troubleshooting system issues and recording bugs in the case there is a system issue during the study session.

One person may fulfill more than one role.

## **8.12 IRB OVERSIGHT**

This study will be conducted under IRB oversight.

## **9. STUDY PROCEDURE**

At the beginning of the test session, subjects will have ample time to read the Informed Consent Form (ICF) and the opportunity to ask questions. The subject will sign the ICF before participating in this study. Once signing the ICF, the subject will be given a unique identifier to protect subject privacy. Subjects may choose to exit the study at any time. They are not required to complete the study if they choose to stop.

Study participants will self-train on how to use the study device using only the available study Pivot Breath Sensor device labeling, including product packaging and Quick Start Guide. A technical support line provided in packaging/Quick Start Guide and the User

Manual will be available should a participant request them. These labeling materials will be available to study participants at any point during the study. Study participants will not be asked to read instructions or use any of the forms of training available except during the knowledge questions covered in the User Documentation Assessment – see Section 11.4. Study personnel will refrain from answering questions on how to use the study device during the study.

Once the study participant has completed the self-training on the Pivot Breath Sensor, they will be asked if they feel ready to proceed with submitting a breath sample. If a participant indicates they do not feel ready, they will be asked to do what they would normally do at home to prepare to use the product and to let the test administrator know when they are ready to submit another sample.

When the participant indicates readiness to provide a breath sample, he/she will be instructed to proceed to provide one breath sample using the study device. After providing this breath sample, the subject will be asked to interpret his/her breath sample result followed by interpretation of other possible breath sample results and the first set of subjective questions. The subjective questions will address the subject's feedback on how giving a breath sample went for them. At which point, the participant will be asked to change the mouthpiece. An optional breath sample may be requested by the moderator followed by interpretation of his/her breath sample result.

Upon completion of these breath sample(s), participants will be asked for subjective feedback, if they experienced difficulty, concerns, or moments of hesitation while using the product, and if they have safety concerns regarding the product or its labeling. Next, they will be assessed for their newly learned knowledge of the device (focused on if CO is “good or bad for you”) and their ability to find and understand information in the product labeling. This is followed by obtaining the participants additional subjective feedback and rating scales.

## 10. DATA COLLECTION

Study personnel will collect information about the participant including

- Age
- Gender
- Race/ethnicity
- Vision
  - Wear glasses?
  - Color blind?
- Hearing
  - Hearing issues?
  - Use a hearing aid?
- Type of smartphone participant uses (iPhone or Android)
- Number of years smoking
- Number of quit attempts over the past 12 months
- Number of cigarettes currently smoked per day

- Smoking history in the past 24 hours
  - Number of cigarettes smoked
  - Time of last cigarette
  - Use of any combustible, inhaled tobacco product other than cigarettes (pipes, cigars, cigarillos, etc.), any electronic cigarette product (e-cigs, vape, vapor), and any other inhaled combustible material
- Attitudes towards smoking
  - Desire to quit
  - Readiness to quit
  - Confidence to quit
  - Perceived difficulty of staying quit
- Current smoking cessation medications
- Participation in a smoking cessation program
  - Past
  - Present
- Breath sensor use (past)
  - Use of CO breath sensors in the past
- Breath sensor use during the study session
  - Model#/Lot# of breath sensor
  - CO measurements

## 11. TECHNICAL APPROACH AND STUDY DESIGN

### 11.1 HUMAN FACTORS AND USABILITY ACCEPTANCE CRITERIA

Each use scenario and user documentation assessment test case will be attributed one of the following assessments for task success:

- Successful: User is able to complete the task safely and effectively. If the user does not complete the task on first try but self-corrects to complete the task without moderator direction or assistance, the task completion may be considered Successful.
- Difficulty: User is able to complete the task safely and effectively, but has significant hesitation or challenges while completing the task. If the user does not complete the task on first try but self-corrects to complete the task without moderator direction or assistance, the task completion may be considered Difficulty.
- Close Call: User is able to complete the task safely and effectively, but performs it in a way that presents the potential for user harm (i.e. near-miss).
- Unsuccessful (Use Error): User is unable to independently complete the task or does not complete the task safely and effectively. Includes instances in which users are unable to complete the task and as a result require study moderator assistance. Instances in which the user self-corrects without requiring moderator assistance do not qualify as unsuccessful.

- Did Not Perform: User does not complete the task for safe and effective use of the device.

At any time, the moderator may remind the participant of the scenario of the testing and the frame of mind they should strive for. A possible reminder may be “Continue to do your best...as a friendly reminder imagine that you are home, that we are not here, and that you just bought this product from the store.” Any instance of study moderator assistance will be noted and assessed depending upon the extent of the assistance provided.

The Pivot Breath Sensor Use FMEA governs Acceptance Criteria for the Pivot Breath Sensor Usability Validation Study. Each hazard-related use scenario observed during usability validation testing will be documented and assessed for risk acceptability as defined in the Use FMEA.

In the case that a hazard-related use scenario is concluded to have an acceptable risk profile per the Use FMEA, its associated test case is considered to “pass.” In the case that a hazard-related use scenario is concluded to have an unacceptable risk profile per the Use FMEA, its associated test case is considered to “fail.” In the case of a failed test case, further risk mitigation and usability evaluation would be required. In the case that further risk mitigation is not possible, a risk-benefit analysis would be documented.

Since there are no critical tasks associated with this product, there is no pre-identified task-specific acceptance criteria related to this study; no use errors were identified that could lead to serious harm. Overall, user performance on each task will be monitored for unforeseen use errors that could lead to serious harm.

## 11.2 STUDY SESSION FORMAT

Each study session will have the following format:

1. Introduction
2. Simulated Use
3. Subjective Feedback
4. Knowledge Tasks
5. User Documentation Assessment
6. Subjective Feedback and Rating Scales

Following a brief introduction each participant will undergo a study session lasting about 60 minutes. The study session will comprise use scenarios, knowledge tasks, user documentation (User Manual and Quick Start Guide) assessment, subjective feedback and rating scales. In addition to the subjective feedback obtained during the defined sections below, subjective feedback may be collected during the use scenarios, knowledge tasks, and User Documentation assessment to inform root cause analysis.

The use scenarios included in the study consider inputs from risk management documentation (Pivot Breath Sensor Use FMEA) to test mitigations to device use (operation) related hazards. Each use scenario is expected to take up to 5 minutes (most will take 2-3 minutes). The use scenarios are listed in Table 2.

The study session will be conducted as a simulated use study where each participant will have access to the study article and will be monitored while performing the use scenarios. Each use scenario is monitored for difficulties, close calls and use errors. The use scenarios will allow for a detailed and focused assessment of the different components of the Pivot Breath Sensor set-up and use.

**Table 2. Use Scenarios for Usability Validation**

ID	Use Scenarios
1	[REDACTED]
2	[REDACTED]
3	[REDACTED]
4	[REDACTED]
5	[REDACTED] ple
6	[REDACTED]

### 11.3 USE SCENARIOS

#### 11.3.1 Use Scenario 1: Self-Selection

- Configuration:

The study moderator presents the participant with the Pivot Breath Sensor device package.

- Prompt:

Take a moment to examine the package. Now I will ask you some questions about whether this product is appropriate for different types of people. (Note: [REDACTED])

1.

2.

3.

### 11.3.2 Use Scenario 2: Start-up device

- Configuration:

The study moderator presents the participant with the Pivot Breath Sensor device package.

- Prompt:

Here is a new Pivot Breath Sensor that has never been used. Please imagine you just bought this product from the store. Given that you just purchased it, you can take as much time as you need to familiarize yourself with the product. Pretend that we are not here. Please start using the product as you normally would at home when you are ready. Feel free to take as much time as you need.

(If user does not begin using device after familiarization period) Please proceed with using the product.

(If the user states they would not use or purchase this product) Let's assume you were given this product to use as a requirement of a smoking cessation program. Take as much time as you need to familiarize yourself with the product. Please start using the product when you are ready.

- Tasks:

- Open the Pivot Breath Sensor packaging
  - Complete Breath Sample

- Prompt:

How did that go for you?

### 11.3.3 Use Scenario 3: Interpret your results – Part 1

- Prompt:

Please walk me through your test results. What does each result mean?

- Tasks:

- Access the CO Log
  - Understand results from the breath tests

Note: This Use Scenario may be continued for interpreting results for Use Scenario 5. (See section 11.3.5 below.)

Expected Response:

For green value:

- [REDACTED]

Or,

- [REDACTED]

Or,

- [REDACTED]

For orange value:

- [REDACTED]

Or,

- [REDACTED]

Or,

- [REDACTED]

For red value:

- [REDACTED]

Or,

- [REDACTED]

Or,

- [REDACTED]

#### 11.3.4 Use Scenario 4: Interpret more results

- Configuration:

The study moderator provides Device with at least three (3) past CO readings having all of the colored CO ppm ranges for the participant to interpret (red, green orange) so participant can interpret colored ppm ranges he/she did not obtain from his/her own breath sample(s).

➤ Study moderator and/or observer to monitor participant [REDACTED]

- Prompt 1:

What does it mean if the result of a person's breath test looks like this? (Moderator points to a green, orange, or red result. An attempt will be made to evenly distribute the order the colors are presented across all groups by counterbalancing.

Counterbalancing scheme will be provided in the final report. Moderator will only ask about results that were not previously covered in Scenario 3)

Expected response: See 11.3.3 response

- Prompt 2:

What does it mean if the result of a person's breath test looks like this? (Moderator points to a green, orange, red or gray result, counterbalanced across participants. Moderator will only ask about results that were not previously covered in Scenario 3)

Expected response: See 11.3.3 response

- Prompt 3:

What does it mean if the result of a person's breath test looks like this? (Moderator points to a green, orange, red or gray result, counterbalanced across participants. Moderator will only ask about results that were not previously covered in Scenario 3) Note that Prompt 3 will be asked unless all result colors were previously covered.

Expected response: See 11.3.3 response

- Prompt 4:

[REDACTED]

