## 6. PIVOT BREATH SENSOR, STUDY DEVICE

The Pivot Breath Sensor comprises a personal mobile breath sensor that measures the level of CO in exhaled breath and displays the exhaled breath CO value to the user directly on the device. The range of CO measurement is 0-100 ppm.

The Pivot Breath Sensor (Figure 1) is portable, battery-powered, and small enough to be conveniently carried by the user throughout the day (pocket, purse, backpack). The Pivot Breath Sensor is rechargeable using a micro-USB cable. The user submits a breath sample by exhaling (blowing) into the mouthpiece of the Pivot Breath Sensor.

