### **6.4 CO LOG**

The CO Log can be accessed from the Pivot Breath Sensor's display screen and shows the most recent exhaled breath CO value in ppm at the top of the screen. The user can view previous values by scrolling within the log (Figure 2).

Values are color coded and can be interpreted by the user with help from the labeling (Figure 3).

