**Figure 2. CO log on Pivot Breath Sensor****Figure 3. Package labeling to interpret results**

## How to interpret your CO sample

Remember: no amount of smoking is safe

Each of your breath sample results is displayed on the sensor screen with a color and a number and are measured in parts per million (ppm).

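### Does the gray result in Use Scenario 4 lack a pre-set correct answer?

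*Combined protocol and SAP*

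**What the plan says.** Use Scenario 4 asks each participant to interpret results that their own breath sample did not produce. The configuration in 11.3.4 calls for at least three stored readings, "having all of the colored CO ppm ranges for the participant to interpret (red, green orange". In Prompt 1, "Moderator points to a green, orange, or red result". In Prompts 2 and 3 the list grows by one: "Moderator points to a green, orange, red or gray result, counterbalanced across participants". All three prompts carry the same scoring line, "Expected response: See 11.3.3 response", and Prompt 3 has a condition: "Note that Prompt 3 will be asked unless all result colors were previously covered".

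The answer key in 11.3.3 has three readable headings, for green, orange and red values, with the answers under each redacted. Section 6.4 says of log entries: "Values are color coded and can be interpreted by the user with help from the labeling (Figure 3". The label text states: "Each of your breath sample results is displayed on the sensor screen with a color and a number". It then gives three bands: 0–6, 7–9 and 10+ ppm. On the instrument itself, section 6 states: "The range of CO measurement is 0-100 ppm". Section 6.3 adds that the log shows an error message, with no color mentioned, when a sample is submitted improperly.

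**The concern.** Gray appears in two prompts and nowhere else in the readable text. A rater scoring a participant's account of a gray result is sent to a section with no visible gray entry, and the set-up does not name a gray reading among those to be loaded. It is also not stated whether gray counts as a color when deciding if Prompt 3 is due.

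Interpretation of results is a stated objective (section 3), and section 12.2.1 treats comprehension answers as objective data judged on criteria fixed in advance. The raters are the sponsor's employees and consultants (section 8.11), and ratings may be revisited after the session. If the correct answer were settled only after responses had been heard, the comprehension finding for that item would carry less weight. Moderators might also ask different numbers of prompts.

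**Working it through.** No figure in the plan needs reproducing; the check compares lists and counts categories.

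**1. Prompts against key and set-up.**
- Shown in Prompts 2 and 3: {green, orange, red, gray}, 4 types.
- Readable headings in 11.3.3: {green, orange, red}, 3 types.
- Named in the 11.3.4 configuration: {red, green, orange}, 3 types.
- Difference in both comparisons: {gray}.

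**2. Is gray a further CO band?** In whole ppm, 0–6 holds 7 values, 7–9 holds 3, and 10–100 holds 91. The sum is 7 + 3 + 91 = 101, which is every whole value from 0 to 100. Nothing is left for gray, so it is not a CO range. The configuration lists CO ranges only, so leaving gray off that list is no contradiction, and a minimum of three readings leaves room for a fourth entry. An error entry of the kind described in 6.3 would fit, but no readable text says that gray means this.

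**3. Is gray a stray word?** Suppose the participant's own sample covers one color in Scenario 3. A three-color scheme then leaves 3 − 1 = 2 results, which Prompts 1 and 2 use up. A four-type scheme leaves 4 − 1 = 3, which matches Prompts 1 to 3. The structure suggests that gray is an intended item and that it counts for the Prompt 3 rule.

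**4. How many responses are involved?** Assume 15 participants (the plan says up to 15), one color covered in Scenario 3, and no result shown twice.
- If gray counts: 15 × 3 = 45 responses, of which 15 are gray.
- If gray does not count, and the Prompt 3 rule looks back to Prompts 1 and 2 as well as Scenario 3: from 15 × 2 = 30 responses with no gray, up to 15 × 3 = 45 with 15 gray.
- If the rule looks back to Scenario 3 only, as the sentence just before it does: Prompt 3 is due for all 15, and the total is 45 again.

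The lower figure of 30 therefore depends on one reading of the rule, and on gray not counting.

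**5. Does any planned result use these counts?** Section 11.1 gives one of five assessments to each use scenario or documentation test case. Section 12.2.1 also assesses by use scenario, citing 11.1 and 11.4. Neither plans a tally by prompt or color, so 30 and 45 are not denominators of any planned summary. Acceptance is governed by risk assessment under the Use FMEA, and section 11.1 states that no acceptance criteria are set for particular tasks because no critical tasks were found.

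**The case for a change.** The strongest case for a change is that redaction does not fully account for the gap. The color headings in 11.3.3 are readable, and the blacked-out answers fall three under each of the three colors, leaving no slot for gray. If the answer sits in Prompt 4 or Table 3, the pointer in Prompts 2 and 3 is still incomplete. The investigator holds equity in the sponsor (section 13), so a pre-set key has particular value, and supplying one would take only a few lines.

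The incomplete pointer stands. The inference to a missing answer does not. Prompt 4, the Knowledge Tasks and most of Table 3 cannot be read, the images of the CO Log and color key are not reproduced, and the Quick Start Guide and User Manual are not in the file. Silence in the remainder is weak evidence. The worry about later re-rating is also tempered by section 12.2.1, which requires each changed rating to be annotated or logged as agreed by study personnel. Low cost alone is not a reason to change a plan when the result would be no sounder for it.

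**Conclusion.** The inconsistency is real but minor: two prompts name a gray result and cite a key whose visible entries cover three other colors. It is a gap that those running the study will fill sensibly. The sponsor designed the display, knows what a gray entry signifies, prepares the sensor or print-out used in the scenario (section 8.8), and can judge whether a participant has understood it.

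The reach is at most one gray item for each of up to 15 participants, inside one of six use scenarios, assuming one color is covered in Scenario 3. The item enters a descriptive assessment with no hypothesis test, no pass mark and no analysis by color. Following the plan as written would not make the study's conclusion unsound. This rests on two assumptions that the readable text cannot confirm: that gray is a defined state of the device, and that the study team shares one understanding of it when rating. Neither is contradicted anywhere in the document.
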